5.5.3 Hypothesis

Ha The ophthalmic solution PRO-174 presents a safety and tolerability profile similar to the comparator in healthy subjects.

Ho The ophthalmic solution PRO-174 presents a safety and tolerability profile different from the comparator in healthy subjects.

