5.6.1 Discussion of the study design

The design of the study (clinical trial) is considered the highest quality standard in the data when it is sought to explore the effect of an intervention. The phase of pharmacological development (phase I) corresponds to the objective of the study which is to assess safety and tolerability, so that the intervention time is short and the sample size required is less than that of a clinical efficacy trial. The presence of parallel groups allows the comparison between the intervention groups on the outcome variables. Blinding and randomisation allow to reduce biases that are incurred with other designs, eg. selection bias, evaluation bias, among others.

6. Material and methods. Participants, interventions and variables

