6.3 Intervention

6.3.1 Managed treatments

6.3.1.1 Treatment under study

The characterization and stability tests of the treatment under study are issued by Sophia Laboratories, S.A. of C.V and will be found in the certificates contained within the master folder of the study.

More detailed information can be found in the researcher's manual.

- PRO-174

- Active substance: Levofloxacin 0.5%
- Pharmaceutical form: ophthalmic solution
- Prepared by: Sophia Laboratories, S.A. of C.V
- Dosage: 1 drop in both eyes, 8 times a day during the waking period
- Description of the solution: transparent solution, free of visible particles.
- Description of container: sterile multi-dose bottle

Table 4. Quali-quantitative formulation of PRO-174

Type of agent	Amount mg/mL	Function
Levofloxacin hemihydrate ⁽¹⁾	5.0	Active principle
Sodium Citrate Dihydrate	Without showing	Additive
Citric acid monohydrate	Without showing	Additive
Disodium Edetate Dihydrate	Without showing	Additive
Sodium chloride	Without showing	Additive
Benzalkonium Chloride ⁽²⁾	0.1	Additive
Fumante Hydrochloric Acid ⁽³⁾	Without showing	Additive
Sodium Hydroxide ⁽⁴⁾	Without showing	Additive
Water for preparation of injectables c.b.p. ⁽⁵⁾	1.0 ml	Vehicle

Quali-quantitative formulation of the product under investigation PRO-174. The concentration of the active ingredients is shown, as well as the substances that act as an additive.

OBSERVATIONS:

(1) Equivalent to Levofloxacin (adjustment made by power).

(2) 50% solution.

(3) 4N hydrochloric acid solution.

(4) 4N sodium hydroxide solution.

(5) c.b.p. (how much is enough for).

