6.3.1.2 Reference treatment

As the reference treatment, a commercially available medication, your batch number and IPP will be kept as proof of the characterization of said product.

- **Sophixín Ofteno®**
 -
 - Active substance: Ciprofloxacin 0.3%
 - Pharmaceutical form: Ophthalmic solution
 - Prepared by: Sophia Laboratories, S.A. of C.V
 - Dosage: 1 drop in both eyes, 8 times a day during the waking period
 - Description of the solution: transparent solution, free of visible particles.
 - Description of container: sterile multi-dose bottle

Table 5. Sophixin Ofteno quali-quantitative formulation

Type of agent	Amount mg/mL	Function
Ciprofloxacin ⁽¹⁾	3.0	Active principle
Boric acid	Without showing	additive
Benzalkonium Chloride ⁽²⁾	0.22	additive
Sodium chloride	Without showing	additive
Disodium edetate dihydrate	Without showing	additive
Water for injection preparation c.b.p. ⁽³⁾	1.0 ml	vehicle

Quali-quantitative formulation of Sophixin Ofteno®. The concentration of the active ingredients is shown, as well as the substances that act as an additive.

OBSERVATIONS:

(1) It is added as Ciprofloxacin Monohydrate.

(2) 50% solution.

(3) How much is enough for.

(4) 4N sodium hydroxide solution.

(5) c.b.p. (how much is enough for).

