8.3 Statistical methodology

8.3.1 Analysis of primary and secondary outcome variables.

The statistical analysis will be carried out by personnel from Sophia Laboratories, S.A. of C.V The statistical program SPSS version 19 (IBM Corporation, Armonk, NY, USA) will be used.

The designated personnel will be blinded to the intervention groups. The coding will be done using consecutive numbers for each intervention group.

The data will be collected and sorted in an excel sheet. Later they will be exported to the platform of the SPSS program. The variables will be categorized according to their nature.

The result of the continuous quantitative variables will be presented in measures of central tendency: media, standard deviation and ranges. **See Table 6.** Scales to be used

The normal distribution of the results will be obtained by the Kolmogorov-Smirnov test.

The statistical analysis of the continuous **quantitative variables** to find significant differences (p) will be the following:

- Intra-group analysis: Wilcoxon rank test.
- Inter-group analysis: Mann-Whitney U test.

The level of difference to consider significance will be of an alpha of 0.05 or less.

The result of nominal and ordinal qualitative variables will be presented in frequencies, proportions and percentages. See table 1 (section 6.4.3).

The statistical analysis to identify significant differences of the **qualitative variables** will be done by creating 2x2 contingency tables and will be done as follows:

- Intra-group difference: McNemar test.
- Difference between groups: test χ^2 (Chi-square) of Pearson.

The level of difference to consider significance will be of an alpha of 0.05 or less.

For the reporting of adverse events all eyes of those participants who were randomly assigned to an intervention group after the baseline visit will be considered. The results will be expressed in number of cases (eyes).

The final report of the results will be shown in tables or graphs, as appropriate.

It will be considered that the investigational drug is safe and tolerable when there are no clinical and statistical differences in all the variables of primary outcome, with respect to its comparators.

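### The safe-and-tolerable rule in 8.3.1 has no direction, so a clear advantage for PRO-174 on one primary variable would withhold the verdict

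*Combined protocol and SAP*

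**What the plan says.** Section 8.3.1 ends with the decision rule: "It will be considered that the investigational drug is safe and tolerable when there are no clinical and statistical differences in all the variables" (meaning the primary ones, judged against the comparator). It names no direction and no margin. Between-group tests are Mann-Whitney U for quantitative variables and Pearson chi-square on 2x2 tables for qualitative ones, each at 0.05. No side is stated for them, and the sample size in 6.6.1 uses 1.96, the two-sided value.

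The hypotheses in 5.5.3 follow the same pattern: "Ha The ophthalmic solution PRO-174 presents a safety and tolerability profile similar to the comparator in healthy subjects", against "Ho The ophthalmic solution PRO-174 presents a safety and tolerability profile different from the comparator in healthy subjects". The general objective in 5.5.1 is to evaluate the safety and tolerability of PRO-174.

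The primary variables are in 6.4.1.1 (six safety items) and 6.4.1.2 (four tolerability items: burning, foreign body sensation, itching, eye comfort index). There are 15 subjects per arm.

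The formulation tables list different preservative amounts in mg/mL: "Benzalkonium Chloride ⁽²⁾ 0.1" for PRO-174 and "Benzalkonium Chloride ⁽²⁾ 0.22" for the comparator.

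**The concern.** A verdict on safety and tolerability should fail when the test product does worse. This one also fails when the product does better. A trial in which PRO-174 caused clearly less burning than a marketed product would have to report, by its own rule, that PRO-174 was not shown to be safe and tolerable. The alternative would be to set the rule aside after seeing the data. Either outcome damages a study that 5.4 describes as the foundation for later clinical studies and as a source of information for regulatory procedures.

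The hypotheses do not rescue the rule. Ho is a different profile, and a better profile is a different one.

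**Working it through.** **Does the text exempt a favourable difference?** The rule in 8.3.1 requires no differences on all primary variables. Ha in 5.5.3 is similarity and Ho is difference. The tests in 8.3.1 have no stated side. The design discussion in 5.6.1 says only that "The presence of parallel groups allows the comparison between the intervention groups on the outcome variables". None of these passages separates better from worse, so an advantage for PRO-174 counts the same as a disadvantage.

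**How often would it matter for one symptom?** The plan gives no figure for the behaviour of its rule, so there is none to reproduce. Inputs:

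- From the plan: n = 15 per arm (6.6), uncorrected Pearson chi-square on a 2x2 table, p ≤ 0.05.
- Assumed: the symptom is scored present/absent once per subject, with true rates p_T (PRO-174) and p_C (comparator).
- Anchors for the low end: 5.3.1.4 puts the most frequent levofloxacin reactions at about 1-3%, and 6.6.1 uses an adverse event rate of 7.3%. The comparator rates in the first three rows are 2.2 times the PRO-174 rate (3 × 2.2 = 6.6; 7.3 × 2.2 = 16.06; 10 × 2.2 = 22). The factor is the ratio of listed preservative amounts, 0.22/0.1, used only to set a spread.

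For every pair of counts a, c from 0 to 15, add Bin(a; 15, p_T) × Bin(c; 15, p_C) over the tables with |z| > 1.96, where z = (a/15 − c/15) / √[p̄(1 − p̄)(2/15)] and p̄ = (a + c)/30. Negative z favours PRO-174.

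| PRO-174 vs comparator | Significant, favours PRO-174 | Significant, against PRO-174 |
|---|---|---|
| 3% vs 6.6% | 0.9% | 0.03% |
| 7.3% vs 16.1% | 7.8% | 0.2% |
| 10% vs 22% | 12.7% | 0.2% |
| 10% vs 30% | 27.7% | 0.04% |
| 10% vs 40% | 51.0% | 0.004% |

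Almost every significant result in these scenarios is an advantage for PRO-174.

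**How large is the smallest significant advantage?** With no cases on PRO-174, 3 of 15 on the comparator gives χ² = 30(15 × 3)²/(15 × 15 × 3 × 27) = 3.33, which is not significant. Four of 15 gives 30(15 × 4)²/(15 × 15 × 4 × 26) = 4.62, which is. A significant advantage therefore means at least 0% vs 27% observed.

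**All primary items, products truly equal.** Treat the ten items as independent, each tested at two-sided 0.05:

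- At least one significant difference: 1 − 0.95¹⁰ = 40.1%.
- At least one favouring PRO-174: 1 − 0.975¹⁰ = 22.4%.

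This is a rough guide. Correlation between items and the discreteness of small tables lower it: at 10% vs 10% the chi-square favours PRO-174 in 1.2% of trials, not 2.5%. Items that hold several measurements, such as the laboratory tests, raise it.

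**The case against.** **The rule may need both kinds of difference.** The wording joins clinical and statistical differences. Read that way, significance alone does not withhold the verdict. This stands: the plan does not define a clinical difference, and the percentages above are chances of statistical significance, so they are upper limits on failure under that reading. It would be too strong to say that any difference, or every significant one, fails the rule. The lack of direction remains under either reading. A significant symptom advantage at this sample size is at least 0% vs 27% observed, which many would call clinical.

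**The effects may be small.** At the rates the plan itself cites, a favourable significant result is uncommon (0.9% to 7.8%). That also stands. Direct questioning about symptoms (6.4.3.8) may give higher rates than adverse event reporting, but the plan offers no figure.

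**The study is exploratory and its specific objectives are descriptive.** True, but 8.3.1 still attaches a formal verdict to the tests.

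**Stronger readings that the documents do not support:**

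- A reader might infer from the benzalkonium chloride amounts that better tolerability of PRO-174 is to be expected. The documents never say what the preservative does to tolerability, most other excipient amounts are not shown, and the active ingredients differ. The amounts show only that the formulations differ.
- A reader might object that the result cannot be attributed to levofloxacin versus ciprofloxacin. The title, objective and hypotheses are about the ophthalmic solution PRO-174, so the plan makes no claim about the molecules.
- A reader might count 30 eyes per arm, which gives larger probabilities. Burning is asked of the subject, and fellow eyes are not independent.

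**Conclusion.** The point holds as a flaw in the decision rule. Sections 8.3.1 and 5.5.3 together withhold the safe-and-tolerable verdict when PRO-174 is clinically and statistically better than its comparator on even one primary variable.

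Its size cannot be fixed from the documents. For one symptom at 15 per arm, the chance of a significant advantage runs from 0.9% to 51.0% over the assumed rates. With equal products it is about 22% for at least one of ten items taken as independent. All of these rest on assumed rates, one present/absent score per subject, and the uncorrected chi-square.

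The flaw does not depend on the preservative difference or on any particular rate. It deserves correction before analysis because the wording is plain and the remedy is cheap.

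**What to change.** In 8.3.1, state that only a difference unfavourable to PRO-174 counts against the verdict, and that favourable differences are reported without blocking it. Align 5.5.3 with this.

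Name the adverse direction for each primary variable: more adverse events, worse visual capacity, higher staining or hyperemia grade, presence of chemosis, more burning, foreign body sensation or itching, and worse comfort index. For measures that can be abnormal either way (intraocular pressure, blood counts, glucose), define adverse as a shift out of the normal range. Use the 11-21 mmHg in 6.4.3 and the laboratory's limits. Because 6.2.1 admits laboratory values up to 10% beyond those limits, say how subjects who start outside them are handled.

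**Cost.** Wording only, with no change to sample size, visits or procedures. The downside is that the verdict becomes easier to obtain. With equal products and ten independent items, the chance of no blocking statistical result rises from 0.95¹⁰ = 59.9% to 0.975¹⁰ = 77.6%. Nor does the change help the trial detect harm: by symmetry with the table, 30% on PRO-174 vs 10% on the comparator is significant in only 27.7% of trials. The report should therefore give the between-group difference with its confidence interval for each primary variable, and should not treat non-significance at 15 per arm as proof of similarity.

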Creation date: August 2016

Phase I clinical study, to evaluate the safety and tolerability of the ophthalmic solution PRO-174 versus Sophixín Ofteno[®], elaborated by Sophia Laboratories, S.A. of C.V. on the ocular surface of ophthalmologically and clinically healthy subjects

Protocol code: SOPH174-0816/I

Protocol version: 1.1

Date of the version: 18/04/2017

Registry: 173301410A0149/2017

Sponsor: Laboratorios Sophia, S.A. de C.V.

1. Summary

Title of the study:	
Phase I clinical study, to evaluate the safety and tolerability of the ophthalmic solution PRO-174 versus Sophixín Ofteno®, elaborated by Sophia Laboratories, S.A. of C.V. on the ocular surface of ophthalmologically and clinically healthy subjects.	
Protocol code:	Creation date:
SOPH174-0816/I	22/08/2016
Protocol version:	Date of the version:
1.1	18/04/2017
Therapeutic indication:	
Eye antibiotic	
Study period:	Development phase: I
3 to 4 months	
Goals:	
To evaluate the safety and tolerability of the formulation PRO-174 manufactured by Sophia Laboratories, S.A. of C.V. on the ocular surface of clinically healthy subjects.	
Hypothesis:	
The ophthalmic solution PRO-174 presents a safety and tolerability profile similar to the comparator in healthy subjects.	
Methodology:	
Phase I clinical trial, controlled, of parallel groups, double blind, randomized, exploratory.	
Number of patients:	
30 subjects, divided into 2 groups [15 subjects (30 eyes) exposed per group]	
Diagnosis and main inclusion criteria:	

 - Signed informed consent. - Systemically and ophthalmologically healthy subjects - Age between 18 to 45 years. -Both genders. - Blood tests [complete blood count (BHc), three element blood chemistry (QS) and liver function tests (PFH)] within normal parameters specified by the reference laboratory with a lower and upper margin of 10%. - Visual capacity 20/30 or better, in both eyes.- -Intraocular pressure ≥ 11 and ≤ 21 mmHg. 	

Test product, dose and route of administration, lot number:
 
 - PRO-174. Levofloxacin 0.5% ophthalmic solution. Prepared by Sophia Laboratories, S.A. of C.V, Zapopan, Jalisco, Mexico. - Dosage: 1 drop every 2 hours during the waking period (8 daily applications), on day 1 and 2; continuing with 1 drop every 4 hours during the waking period (4 daily applications) from day 3 to 7. Both eyes. - Route of administration: ophthalmic

Duration of treatment: 7 days

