
Reference product, dose and route of administration, lot:
 
 - Sophixin Ofteno. Ciprofloxacin 0.3% ophthalmic solution. Prepared by Laboratories Sophia, S.A. of C.V., Zapopan, Jalisco, Mexico. - Dosage: 1 drop every 2 hours during the waking period (8 daily applications), on day 1 and 2; continuing with 1 drop every 4 hours during the waking period (4 daily applications) from day 3 to 7. Both eyes. - Route of administration: ophthalmic

Evaluation criteria:
 
Primary security outcome variables:
 
 - Presence of adverse events. - Intraocular pressure. - Visual ability - Laboratory tests: BHc, QS and PFH. - Ocular surface staining with fluorescein and lissamine green using Oxford scale - Ophthalmological signs: conjunctival hyperemia, chemosis. 
Primary outcome variables of tolerability:
 
 - Burning - Foreign body sensation - Itching - Eye comfort index 
Primary outcome variables of tolerability:
 
 - Burning - Foreign body sensation - Itching - Eye comfort index

Statistical methodology:
 
The data will be expressed with measures of central tendency: mean and standard deviation for the quantitative variables. The qualitative variables will be presented in frequencies and percentages. The statistical analysis will be carried out through the Mann-Whitney U test for quantitative variables for the difference between the groups. The intra-group difference will be made with the Wilcoxon rank test. The difference between the qualitative variables will be analyzed by means of X² (Chi²). An alpha ≤ 0.05 will be considered significant.

2. Content

1. SUMMARY	1
2. CONTENT	3
3. INDEX OF ABBREVIATIONS	7
4. ADMINISTRATIVE STRUCTURE OF THE STUDY	9
5. INTRODUCTION	11
5.1 THEORETICAL FRAMEWORK	11
5.2 DEFINITION OF THE PROBLEM AND FUNDAMENTAL REASON	12
5.3 BACKGROUND	12
5.3.1 LEVOFLOXACINO	12
5.3.1.1 Pharmacodynamic properties	13
5.3.1.2 Pharmacokinetics in ophthalmic application	14
5.3.1.3 Clinical efficacy	14
5.3.1.4 Security	16
5.4 JUSTIFICATION	16
5.5 OBJECTIVES AND HYPOTHESIS	16
5.5.1 GENERAL OBJECTIVE	16
5.5.2 SPECIFIC OBJECTIVES	16
5.5.3 HYPOTHESIS	17
5.6 STUDY DESIGN AND PLAN	17
5.6.1 DISCUSSION OF THE STUDY DESIGN	18
6. MATERIAL AND METHODS. PARTICIPANTS, INTERVENTIONS AND VARIABLES	18
6.1 STUDY CENTER	18
6.1.1 ORGANIZATION OF THE CENTER	18
6.1.2 DOCUMENTATION TO BE DELIVERED TO SPONSOR	19

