6.4.3 Methods and scales to be used for the measurement of the variables

Variable	Unity	Symbol	Type	Measuring method	Normal value
Age	Years	--	Continuous	Calculation from the date of birth	NA
Gender	Female/ Male	F / M	Nominal	Direct questioning	NA
Adverse events	Number of cases	n	Discreet	Count	NA
Intraocular pressure	Milimeters of mercury	mmHg	Continuous	Goldman's applanation tonometry	11 - 21
Visual ability	Fraction	Snellen	Nominal	Primer	
Tear rupture time	Seconds	s	Continuous	Direct count	> 10
Eye comfort index	points	--	Discreet	Questionnaire	
	Present / Absent	--	Nominal	Comprehensive valuation	Absent
Vital signs					
Heart rate	Beats per minute	lpm	Discreet	Auscultation	60 – 100
Breathing frequency	Breaths per minute	rpm	Discreet	Auscultation	12 – 24
Systemic blood pressure	Milimeters of mercury	mmHg	Continuous	Non-invasive auscultatory measurement	< 120 / 80
Previous segment					
Ocular surface staining	Degrees	--	Discreet	Direct observation with fluorescein and green lysamin stain	Oxford Scale
Ophthalmologic signs and symptoms					

Variable	Unity	Symbol	Type	Measuring method	Normal value
Conjunctival hyperemia	Normal / Very Light / Mild / Moderate / Severe	--	Ordinal	Direct observation. Classification of Efron.	Normal
Chemosis	Present / Away	--	Nominal	Direct observation	Absent
Burning	Severity: Absent, very mild, mild, moderate and severe	--	Nominal	Direct questioning	Absent
Foreign body sensation	Severity: Absent, very mild, mild, moderate and severe	--	Nominal	Direct questioning	Absent
Pruritus	Frequency: At all times, almost at all times, 50% of the time, almost in no time, at any time	--	Nominal	Direct questioning	Absent
Posterior segment					
Macula	Normal / Abnormal	--	Nominal	Direct observation	Normal
Optical disk integrity	Normal / Abnormal	--	Nominal	Direct observation	Normal
Blood count					
Erythrocytes		M/uL	Continuous		
Hemoglobin	Grams over deciliter	g/dL	Continuous		
Hematocrit	Percentage	%	Continuous		
VGM	Femto liters	fL	Continuous		

Variable	Unity	Symbol	Type	Measuring method	Normal value
HCM	picograms	pg	Continuous		
CMHbG	Grams over deciliter	g/dL	Continuous		
Leukocytes	Thousands per liter units	Mil/uL	Continuous		
Platelets	Thousands per liter units	Mil/uL	Continuous		
Myelocytes	Percentage	%	Discreet		
Metamyelocytes	Percentage	%	Discreet		
Bands	Percentage	%	Discreet		
Segmented	Percentage	%	Discreet		
Lymphocytes	Percentage	%	Discreet		
Monocytes	Percentage	%	Discreet		
Eosinophils	Percentage	%	Discreet		

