6.4.3.10 Pregnancy test

It refers to the performance of a rapid pregnancy test in all women of childbearing age who wish to enter the study. By fertile age we understand women who have not had their menopause, defined as 12 months since the last menstrual period in women over 40 years of age; or those who underwent bilateral hysterectomy or oophorectomy. Women of childbearing age with contraceptive methods including bilateral tubal obstruction should be tested for pregnancy. This test will be carried out by the IP or the designated team person according to the instructions of the device delivered by the sponsor. When applicable, the completion, result and date must be registered in the CRF. If you do not apply, you must write down the reason.

6.4.3.11 Lab tests.

The PI will deliver to the subject the order of the studies of BH, QS and PFH, to be carried out in the clinical laboratory designated by the sponsor. The clinical laboratory will deliver to the IP the results for its assessment and registration. The normal parameters to be considered will be the ranges established by the laboratory, Nevertheless the clinical criterion of the PI will prevail in the decision of normality or abnormality of the results.

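### The safe-and-tolerable verdict in 8.3.1 treats non-significant difference tests as evidence of similarity, with no margin, interval criterion or clinical threshold

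*Combined protocol and SAP*

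**What the plan says.** **Hypotheses.** Section 5.5.3 states: "Ha The ophthalmic solution PRO-174 presents a safety and tolerability profile similar to the comparator in healthy subjects". The null is the opposite: "Ho The ophthalmic solution PRO-174 presents a safety and tolerability profile different from the comparator in healthy subjects". The synopsis repeats the similarity hypothesis.

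**Tests.** The synopsis says: "The statistical analysis will be carried out through the Mann-Whitney U test for quantitative variables for the difference between the groups". Section 8.3.1 adds Pearson chi-square for qualitative variables. Each test is judged at 0.05.

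**Decision rule.** Section 8.3.1 will regard the investigational drug as "safe and tolerable when there are no clinical and statistical differences in all the variables of primary outcome, with respect to its comparators".

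**Clinical references.** These concern individuals: normal values in Table 6 of 6.4.3, and in 6.4.3.11 the statement that "the clinical criterion of the PI will prevail in the decision of normality or abnormality of the results". Section 9.2 has a group-level limit on serious adverse events (more than 5% of participants), but as a trigger for early termination.

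**Adverse events.** Table 6 records them as a count ("Number of cases"), and 8.3.1 reports them by eye. Neither says which test applies.

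**Purpose.** Section 5.6 labels the trial exploratory, and every objective in 5.5.2 is to describe. Section 5.4, on the development of PRO-174, names regulatory procedures and commercialization as uses of the information the sponsor generates.

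**The concern.** Mann-Whitney and chi-square can only produce evidence of a difference. When they do not, the data may be compatible with no difference, with a large one, or with both. The plan nevertheless turns that outcome into a positive verdict. The clinical half of the rule has no pre-specified content, so the p-value is the only part that can be applied reproducibly.

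The sentence also has two readings. On the plain one, both kinds of difference must be absent, so a single p of 0.05 or less in any primary variable fails the product, with no handling of multiplicity. On the other, only a difference that is both clinical and statistical counts, and the undefined clinical part decides.

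At stake is the headline conclusion. Someone following the plan exactly could report PRO-174 as safe and tolerable mainly because the groups are small.

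**Working it through.** **The plan's own calculation.** Section 6.6.1 uses a formula for a difference between two proportions (1.96 and 0.84) and states 12.5 per group. The second proportion is not clearly defined. Taking 0.073 v 0.60, the usual pooled formula gives 11.4, rounded up to 12, and the unpooled one gives 8.7. Taking 0.40 instead gives 26 or 22.6. No variant tried gives exactly 12.5. On any reading the trial is sized to detect a difference, not to show similarity. Nothing below depends on resolving the 12.5.

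**Inputs.** 15 subjects (30 eyes) per group, two-sided 0.05, and a base rate of 7.3%, all from 6.6.1. That section attributes the 7.3% to a preservative-free solution that is neither study product. The alternative rates and the between-eye correlations are assumptions.

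**Chance of significance.** Sum Pr(X = x) × Pr(Y = y) over all pairs (x, y) for which Pearson chi-square, without continuity correction, gives p of 0.05 or less. For subjects, X and Y are binomial with n = 15. For eyes, each subject contributes 0, 1 or 2 events, with P(both eyes) = p² + ρp(1 − p).

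| Rate v 7.3% | Eyes, ρ = 0 | Eyes, ρ = 0.5 | Eyes, ρ = 1 | Subjects |
|---|---|---|---|---|
| 7.3% (type I error) | 4.6% | 10.1% | 20.8% | 1.3% |
| 21.9% | 37.5% | 41.1% | 47.1% | 17.6% |
| 40% | 88.5% | 84.3% | 82.0% | 60.7% |
| 60% | 99.8% | 99.0% | 98.0% | 92.6% |

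A tripled rate is therefore non-significant 62%, 59%, 53% and 82% of the time, in column order. The last two eye columns detect more partly because ignoring the pairing inflates the type I error. An 80% chance of detection needs a rate of about 36%, 37%, 39% and 50% respectively.

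**If Mann-Whitney is used on counts.** Simulated Poisson counts with the same incidences (60,000 runs) give nearly the same non-significance at the tripled rate: 62% (independent eyes), 53% (concordant eyes) and 83% (subjects).

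**Worked example, 4/15 v 1/15.** X² = 30 × (4 × 14 − 11 × 1)² / (5 × 25 × 15 × 15) = 2.16, so p = 0.142. The Wilson limits are 0.109 to 0.520 for 4/15 and 0.012 to 0.298 for 1/15. The Newcombe interval for the difference of 0.200 is:

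- lower: 0.200 − √[(0.267 − 0.109)² + (0.298 − 0.067)²] = −0.080
- upper: 0.200 + √[(0.520 − 0.267)² + (0.067 − 0.012)²] = 0.459

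The rule would record no statistical difference, although the interval reaches 46 points.

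**No events at all.** 0/15 v 0/15 gives a Newcombe interval of about ±20 points. The two-sided 95% upper limit for 0/15 alone is 1 − 0.025^(1/15) = 21.8%.

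**The opposite error, on the plain reading only.** The plan lists ten primary items (six safety, four tolerability). If they were independent with 5% error each, a product identical to the comparator would fail with probability 1 − 0.95^10 = 40%. Simulation gives 35% and 29% at assumed correlations of 0.3 and 0.5. Rare binary items reject less often than 5%, and eye-level items that ignore pairing reject more often.

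**The case against.** The strongest reply is that this is a small exploratory phase I study whose objectives are purely descriptive. Group summaries will be reported alongside the p-values, and the fault lies in one sentence plus the hypothesis wording. All true, but this argues for the change: a descriptive study has no need of a pass/fail verdict from significance tests.

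A second reply is that the rule also requires no clinical difference, which medical staff could judge. They could, but nothing pre-specified says what would count, so the judgement is not a criterion. The 5% serious-adverse-event limit in 9.2 does not fill the gap, because it does not compare the groups.

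Third, the illustration covers one of ten primary items and uses a borrowed base rate and an assumed effect. That stands: the figures show how weak the evidence from non-significance is, not how often the whole rule would be passed wrongly. The 40% is likewise conditional. Laboratory tests cover many analytes and staining uses two dyes, so ten is not the true number of tests.

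Finally, 5.4 speaks of information the sponsor generates for its products in general. Regulatory use of this particular verdict is a reasonable inference rather than an explicit statement.

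**Conclusion.** The point holds. The planned tests cannot reject the stated null, and nothing in the documents supplies a between-group margin, interval criterion or clinical threshold, so the 8.3.1 verdict rests on non-significance. That conclusion follows from the text and needs no assumed effect size.

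The practical weight is large for moderate effects: roughly half to four-fifths of trials would miss a tripled adverse event rate, depending on the unit of analysis. It is small for very large effects, since a 60% rate would be detected at least 93% of the time. These figures rest on the 7.3% base rate, the assumed alternatives and the assumed between-eye correlations. The ambiguous wording is a further reason to rewrite the sentence.

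**What to change.** Delete the verdict sentence in 8.3.1 and replace it with, for example: *Results will be described by group. For each primary variable the between-group difference will be reported with its 95% confidence interval, using the subject as the unit or a method that allows for the two eyes of a subject. A non-significant test will not be taken as evidence of similarity.*

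Restate the hypothesis in 5.5.3 and the synopsis descriptively, in line with 5.5.2 and 5.6. Keep a similarity claim only for named variables that have a justified, pre-specified margin and an interval criterion, with the null that the difference is at least the margin.

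The cost is wording in three places and a weaker claim, with no new subjects or data. A margin-based claim would cost more. For non-inferiority with a true rate of 7.3% in both groups, one-sided 0.025 and 80% power, n per group = (1.96 + 0.84)² × 2 × 0.073 × 0.927 / margin². This gives about 107, 48, 27, 17 and 12 for assumed margins of 10, 15, 20, 25 and 30 points. These are normal approximations and rough at about one expected event per group, but they show that 15 per group supports only a wide margin.
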